12.4.5 Time to First Subsequent Therapy

Time to First Subsequent Therapy (TFST) will be estimated and summarized using Kaplan-Meier methodology. If no new subsequent anti-cancer treatment is observed, the TFST will be censored at the last visit in the trial. The TFST-results will be presented in the same way as for DoR.

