6.2 Secondary Endpoints

1. ORR after 2 cycles defined as the proportion of patients obtaining a centrally assessed CR or PR according to the INRC at completion of two treatment cycles
2. Duration of response (DoR), defined as the time from first centrally assessed OR (CR or PR according to the INRC) to PD or death
3. CR rate, defined as the proportion of patients obtaining a centrally assessed CR according to the INRC at or before completion of four treatment cycles
4. CR rate after two cycles defined as the proportion of patients obtaining a centrally assessed CR according to the INRC at completion of two treatment cycles
5. Minor response (MR) rate, defined as the proportion of patients obtaining a centrally assessed MR according to the INRC at or before completion of four treatment cycles
6. "MR or better" rate, defined as the proportion of patients obtaining a centrally assessed CR, PR or MR according to the INRC at or before completion of four treatment cycles
7. Proportion of patients with disease in BM at enrollment who obtain centrally assessed CR in BM and convert to minimal residual disease (MRD) negative (assessed by reverse transcriptase-quantitative polymerase chain reaction (RTqPCR)) at or before completion of four cycles
8. Time to First Subsequent Therapy or death (defined as the time from initiation of treatment with investigational medicinal products (IMP) until death or start of new anti-cancer treatment (prohibited as per protocol))
9. PFS defined as the time from first IMP administration until centrally assessed PD or death, whichever comes first
10. OS defined as the time from first IMP administration until death
11. 1- and 2-years PFS defined as the proportion of patients alive and with no centrally assessed PD at 1- and 2 year, respectively after first IMP administration
12. 1- and 2-year OS defined as the proportion of patients alive at 1- and 2 years after first IMP administration
13. Safety incl. incidence of AEs and SAEs graded according to Common Terminology Criteria for AEs (CTCAE) version 5.0
14. Pain during naxitamab infusions as assessed by Wong Baker- and FLACC scales
15. Incidence of ADA (including assessment for neutralizing potential and time to first positive ADA assessment from first day of naxitamab administration)
16. Number of naxitamab infusions done in an out-patient setting defined as infusions not requiring admission to hospital due to adverse events

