12.4.3 Duration of response

The DoR, in patients with OR, will be estimated and summarized using Kaplan-Meier methodology. If no progression or death event is observed, DoR will be censored at the time of the last response assessment. The DoR will be censored if:

- more than one assessment visit in a row is missed, or
- an anti-cancer therapy other than naxitamab and IT is administered (ignoring allowed therapies and procedures such as radiotherapy or surgery of the primary site, cf. Section 8.4.7 for details).

The distribution of the DoR will be summarized by estimates and two-sided 95% confidence intervals of the first, second and third quartiles. The number of patients with events and the number of censored patients will be presented. The reasons for censorings will be summarized.

Summary tables will be presented for the FAS and PPS. The DoR will be presented in patient data listings including the onset of response date, observed event date, censoring flag, censoring date and censoring reason. The results will be presented for both central and local evaluation. The latter will be considered exploratory.

12.4.4 Rate of patients who obtain CR in BM and convert to MRD negative

The proportion of patients with disease in BM at enrollment who obtain CR in BM and convert to MRD negative at or before completion of four cycles will be analyzed and

presented in the same way the primary endpoint for the sub-population of patients who are BM MRD positive at baseline, for the FAS and PPS.

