12.4.6 PFS and OS

PFS will be censored in the same way as DoR. If no death event is observed, OS will be censored at the date of the last assessment. PFS and OS will be estimated using Kaplan-Meier methods and presented in same way as DoR. In addition, the Kaplan-Meier estimates of the proportions, together with the corresponding CIs, of patients without progression or death (PFS) and alive (OS) at 1 and 2 years will be presented for the two endpoints respectively. The PFS results will be presented for both central and local evaluation. The latter will be considered exploratory.

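### TFST is defined with death as an event, but Section 12.4.5 censors patients who die without new therapy, which biases the Kaplan-Meier estimate upward

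*Combined protocol and SAP*

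**What the plan says.** **Definition.** Section 6.2, item 8, names the endpoint "Time to First Subsequent Therapy or death" and runs it from the start of IMP "until death or start of new anti-cancer treatment (prohibited as per protocol"). The synopsis gives the same definition under its key secondary endpoints.

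**Analysis.** Section 12.4.5 first states: "Time to First Subsequent Therapy (TFST) will be estimated and summarized using Kaplan-Meier methodology". It then gives one censoring rule: "If no new subsequent anti-cancer treatment is observed, the TFST will be censored at the last visit in the trial". Death is not mentioned. The section closes with "The TFST-results will be presented in the same way as for DoR".

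**Neighbouring endpoints.** Three other rules in Section 12.4 do account for death:
- DoR (12.4.3): "If no progression or death event is observed, DoR will be censored at the time of the last response assessment".
- PFS (12.4.6): "PFS will be censored in the same way as DoR".
- OS (12.4.6): "If no death event is observed, OS will be censored at the date of the last assessment".

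**The concern.** A patient who dies without starting new therapy satisfies both texts, and they give opposite results: an event under Section 6.2, a censored observation under Section 12.4.5. A programmer who follows the analysis section literally will censor these deaths at the last visit before death.

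That changes the quantity estimated. With deaths censored, Kaplan-Meier targets the time to new therapy in a hypothetical setting where nobody dies first. The endpoint as defined is the time alive and free of new therapy. The misclassified patients are those who did worst. The trial has a single arm, so no control group shares the distortion, and the TFST median and curve will be read at face value.

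**Working it through.** **1. Can other text supply the missing condition?**
- The link to DoR in Section 12.4.5 covers presentation only. PFS, by contrast, expressly takes over DoR's censoring.
- DoR's censoring could not be carried over whole in any case. Section 12.4.3 censors DoR when another anti-cancer therapy is given, and for TFST that is an event.
- Section 12.13 leaves further detail to the SAP. Nothing in the combined document corrects the TFST rule.

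**2. The plan's own figures.** The plan states no expected value for TFST. Its sample-size figure reproduces: the exact two-sided binomial test of 20% against 40% with 41 patients rejects at 14 or more responses and has power 0.8219 (stated 82%), and 41/(1 − 0.20) = 51.25, rounded up to 52. None of this depends on TFST.

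**3. Direction.** Let S(t) be the probability of being alive and free of new therapy. Let d be the share of first events that are deaths without new therapy, constant over time. Kaplan-Meier with those deaths censored estimates S(t)^(1−d). This exceeds S(t) for any d above 0 and equals it when d = 0.

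**4. Size, first illustration.** Inputs, all assumed:
- Constant hazards.
- A composite median of 9.2 months, borrowed from the median time to progression that Section 4.3.4 quotes for the Spanish compassionate-use series of the same combination. It is not a TFST figure.
- d from 5% to 40%.

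Hazard = ln 2/9.2 = 0.0753 per month, so S(12) = exp(−0.904) = 40.5%. Under the written rule the 12-month value is 0.405^(1−d) and the median is 9.2/(1−d).

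| d | 12-month, as defined | 12-month, as written | Median, as written (months) |
|---|---|---|---|
| 5% | 40.5% | 42.4% | 9.7 |
| 10% | 40.5% | 44.3% | 10.2 |
| 20% | 40.5% | 48.5% | 11.5 |
| 30% | 40.5% | 53.1% | 13.1 |
| 40% | 40.5% | 58.1% | 15.3 |

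Over the same range of d, the 12-month excess is 1.8 to 18.5 points with an assumed median of 6 months, and 1.8 to 16.0 points with 12 months.

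**5. Size, second illustration.** Fix the new-therapy hazard at an assumed 0.06 per month and let the death hazard be 0.01, 0.02 or 0.03, so that deaths are 14%, 25% or 33% of first events.
- Median as defined: ln 2/0.07 = 9.9, ln 2/0.08 = 8.7 and ln 2/0.09 = 7.7 months. As written: ln 2/0.06 = 11.6 months in every case.
- 12-month proportion as defined: exp(−0.84) = 43%, exp(−0.96) = 38% and exp(−1.08) = 34%. As written: exp(−0.72) = 49% in every case.

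The written rule therefore returns the same answer however many patients die untreated.

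**6. Simulation.** The formula assumes censoring at the time of death, whereas the rule censors at the last visit before it. In 1,000 simulated trials of 52 patients (9.2-month median), with deaths censored at the last visit, the mean 12-month estimate rose from 0.407 to 0.425 (d = 5%), 0.403 to 0.439 (10%), 0.403 to 0.481 (20%), 0.406 to 0.529 (30%) and 0.407 to 0.579 (40%). The written rule gave the lower value in 2.1% of trials at d = 5%, 0.4% at d = 10% and none at 20% or more.

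**The case against.** The best reply is that Section 12.4.5 is merely incomplete. It does not say that deaths are censored. Section 6.2 sets the events, and censoring ordinarily applies only to patients without one. That may well be what the authors meant, but the sentence states a condition that a patient who died untreated meets, and the neighbouring rules show that death was written in where it was wanted.

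Other points carry some weight:
- **The SAP may settle it.** Section 12.13 promises more detail on the analyses already described, which is not a correction of them.
- **The error would be visible.** TFST is to be presented as DoR is, with reasons for censoring and listings, and OS and PFS are reported alongside. A death coded as censored could be found there, but the headline estimate would still be wrong.
- **The size is assumed.** This stands. With no such deaths the bias is zero. At 5% to 10% it is about 2 to 4 points at 12 months, well inside a rough 95% interval of ±13 points for a proportion near 40% in 52 patients. Larger shares are not negligible, and unlike sampling error this shift is systematic.
- **TFST is descriptive.** This also stands. There is no test, threshold or hierarchy attached to it.

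**Conclusion.** The contradiction is established from the text alone: the same patient is an event in the synopsis and Section 6.2 and censored in Section 12.4.5. Applied as written, the rule overstates TFST on average whenever any patient dies before new therapy. Some such deaths are very likely: Section 4.1 cites a 1-year OS of 57% in a meta-analysis of early-phase trials, and Section 4.3.4 cites 55% with this combination in heavily pretreated patients. How many of those deaths preceded new therapy is not stated, so the overstatement of about 2 to 18 percentage points at 12 months (d from 5% to 40%, 9.2-month composite median, constant hazards) is an illustration and not a prediction. The primary ORR analysis, the sample size and the power are not affected. What needs correcting is the rule for one key secondary endpoint.

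**What to change.** Replace the censoring sentence in Section 12.4.5 with: *Death from any cause and start of new anti-cancer treatment are events, whichever comes first. Patients alive without new anti-cancer treatment are censored at the last date on which they were known to be alive and free of new treatment.* Carry the same wording into the SAP and use the Section 6.2 name for the endpoint throughout.

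The essential change is to make death an event. The revised censoring date is secondary: it ties censoring to the two facts that a composite endpoint needs, survival and treatment status.

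If a therapy-only endpoint is what is wanted, change the definitions in the synopsis and Section 6.2 instead, and estimate cumulative incidence with death as a competing event.

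The cost is one sentence. Deaths and new anti-cancer therapy are already collected through long-term follow-up (Section 3, Table 1 footnote on long-term follow-up; Section 7.8). No extra visits, data or patients are needed.

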12.4.6 PFS and OS

PFS will be censored in the same way as DoR. If no death event is observed, OS will be censored at the date of the last assessment. PFS and OS will be estimated using Kaplan-Meier methods and presented in same way as DoR. In addition, the Kaplan-Meier estimates of the proportions, together with the corresponding CIs, of patients without progression or death (PFS) and alive (OS) at 1 and 2 years will be presented for the two endpoints respectively. The PFS results will be presented for both central and local evaluation. The latter will be considered exploratory.

12.4.7 Exploratory Endpoints

The analyses of the exploratory endpoint will be described in the SAP.

12.5 Safety Analysis

The SAF will be used for the safety analyses. The overall observation period will be divided into 3 parts:

1. pre-treatment period: from day of patient's informed consent to the day before first dose of IMP
2. on-treatment period: from day of first dose of IMP to 42 days after last dose of IMP
3. post-treatment period: starting at day 43 after last dose of IMP.

If dates are incomplete in a way that clear assignment to pre-, on-, post-treatment period cannot be made, then the respective data will be assigned to the on-treatment period.

Additional analyses and presentations will be included in the SAP.

12.5.1 Adverse events

AE data will be presented descriptively in summary tables and listings. AEs will be regarded as Treatment-Emergent AEs (TEAEs) if they occur after start of first IMP administration.

An infusion/administration related TEAE is an AE that occurs on a day of IMP administration (after start of IMP administration) and is considered related to the IMP treatment.

An infusion related hypersensitivity TEAE is an AE that match a selected list of hypersensitivity terms based on reported preferred terms (including the MedDRA SMQ narrow scopes of anaphylactic reaction, angioedema, hypersensitivity and severe cutaneous reaction), that occurs on a day of naxitamab infusion (after the infusion start) or the day after a naxitamab infusion irrespectively of relatedness to naxitamab.

AEs with onset during the pre- and post-treatment period will be listed. AEs with onset during the on-treatment period will be summarized as follows: summaries of AEs will be presented for all TEAEs, IMP-related TEAEs, CTCAE Grade 3 or higher TEAEs, IMP-related CTCAE Grade 3 or higher TEAEs, infusion/administration-related TEAEs, infusion-related hypersensitivity TEAEs, SAEs, IMP-related SAEs, CTCAE Grade 3 or higher SAEs, IMP-related CTCAE Grade 3 or higher SAEs, TEAEs leading to treatment discontinuation, AEs leading to death.

12.5.2 Safety laboratory data

Descriptive statistics will be presented for baseline values, absolute values, and changes from baseline in safety laboratory parameters. Laboratory data will be summarized in tables and presented in figures by type of laboratory test.

12.5.3 Vital signs

Changes from baseline in vital signs will be presented in summary tables.

12.6 Pain assessments during naxitamab infusions

Pain scores will be presented in summaries and listings.

12.7 Analysis of ADA Formation

ADA data will be presented in summary tables and listings. For subjects who develop ADA during the trial, time to first positive ADA assessment from first day of naxitamab administration will be presented in a figure.

12.8 Hospitalization days

The number of hospitalization days will be presented in summary tables and listings.

12.9 Naxitamab infusions in out-patient setting

The number of naxitamab infusions in out-patient setting will be presented in summary tables and listings.

12.10 Interim Analysis

Ad-hoc interim analyses may be performed in relation to health authority interactions.

12.10.1 Multiplicity adjustments

No multiplicity adjustments will be made.

12.11 Subgroup Analyses

The primary endpoint will be analyzed and presented for the following subgroups:

- primary refractory vs. first relapse vs first PD during frontline therapy
- soft tissue lesions present at baseline (yes / no)
- tumor MYCN amplification status (yes / no)
- prior exposure to anti-GD2 antibody therapy (yes / no)
- ADA status (negative at all times / positive at any time)
- disease compartment (bone, BM, bone and BM combined (*i.e.*, OR excl. soft tissue lesions) as well soft tissue)
- geographical region

- site
- age group (0 - <2, 2 - <6, 6 - <12, 12 - <18 and >=18 years)
- body weight group (<20 kg; 20-<50 kg; >=50 kg)
- sex (male/female)
- race

Overviews of AEs will be presented for the following subgroups:

- primary refractory vs. first relapse vs first PD during frontline therapy
- ADA status (negative at all times / positive at any time)
- geographical region
- age group (0 - <2, 2 - <6, 6 - <12, 12 - <18 and >=18 years)
- body weight group (<20 kg; 20-<50 kg; >=50 kg)
- sex (male/female)
- race

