6 ENDPOINTS

6.1 Primary Endpoint

ORR, defined as the proportion of patients obtaining a centrally assessed CR or PR according to the International Neuroblastoma Response Criteria (INRC) at or before completion of four cycles.

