7.2.1 Treatment

[figure not shown]
Each treatment cycle is 21 days. Patients will receive irinotecan 50 mg/m²/day IV and temozolomide 100 mg/m²/day orally (both on Days 1-5) in combination with naxitamab 2.25 mg/kg/day IV (Days 2, 4, 8 and 10) (total 9 mg/kg per cycle), and GM-CSF 250 μ g/m²/day sc, (Days 6-10). Patients will receive up to 18 IT cycles after enrollment. Naxitamab and GM-CSF will be given for at least 8 cycles.

Patients who discontinue IT due to unacceptable toxicity will be offered treatment with naxitamab + GM-CSF alone. The treatment will be administered in 28-days cycles with naxitamab 3.0 mg/kg/infusion at Days 1, 3 and 5 and GM-CSF 250 μ g/m²/day for 5 days from Days -4 to 0, and at 500 μ g/m²/day for 5 days from Day 1 to Day 5. The total number of naxitamab treatment cycles will be at least 8 cycles (including the cycles given in the HITS regimen).

Patients who discontinue GM-CSF due to unacceptable toxicity should continue naxitamab treatment.

Patients achieving a CR or PR (both patients receiving HITS or naxitamab + GM-CSF alone) should receive 8 naxitamab cycles or 5 additional naxitamab cycles following the objective response, whichever provides the longest treatment with naxitamab. Patients who have achieved a MR or SD at completion of the 8 cycles (both patients receiving HITS or naxitamab + GM-CSF alone) may receive naxitamab + GM-CSF consolidation treatment for 5 cycles administered at every 6 weeks (in the HITS regimen) or 8 weeks (in the naxitamab + GM-CSF alone regimen). The total number naxitamab cycles to be administered includes the treatment cycles administered in the HITS regimen.

Figure 1 Trial design

*each cycle is 21 days, ** each cycle is 28 days

¹Patients achieving a CR or PR should receive at least 8 naxitamab cycles or 5 additional naxitamab cycles following the objective response, whichever provides the longest treatment with naxitamab

² Patients should receive at least 8 cycles of naxitamab + GM-CSF including the cycles in the HITS regimen

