7.8 Follow-up

EOT assessments should take place minimum 6 weeks (up to 10 weeks) after last treatment. If treatment is discontinued due to PD, planned initiation of new anti-NB treatment prohibited as per protocol, withdrawal from the trial or investigator judges it warranted due to medical reasons/non-compliance, the patient should be called for EOT visit as soon as possible and before initiation of new anti-NB treatment. The patients should subsequently be followed for safety and new anti-cancer therapy for a total of 6 weeks after last treatment (see flowchart in Section 3 and treatment discontinuation criteria in Section 7.12).

After EOT, a long-term FU period will start. The patient will attend long-term FU visits approximately every 4 months for up to 2 years after EOT.

The investigator will perform response assessments (if the patient has not experienced PD) (see Section 3, 9.1.1, 9.1.2 and [Appendix 2](#)), report death and PD (as applicable) and collect information on SAEs ongoing at EOT visit, new SAEs at least possibly related to naxitamab treatment, secondary malignancies, and autoimmune diseases. Furthermore, new anti-cancer therapy should be collected as concomitant medication. Please refer to flowcharts in Section 3 and [Appendix 2](#).

Trial period completion is defined as when the patient has completed the final scheduled visit (long-term FU visit 2 years after EOT).

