7.12 Premature Discontinuation of Treatment

General discontinuation criteria

A patient should be discontinued from treatment with all IMPs if any of the following situations occur:

1. Grade 4 anaphylaxis related to naxitamab
2. Grade 3 anaphylaxis related to naxitamab not responding to medical intervention at the discretion of the investigator
3. Grade 4 sensory neuropathy or Grade 3 sensory neuropathy that interferes with daily activities for more than 2 weeks at the discretion of the investigator
4. CTCAE Grade 3 pain unresponsive to maximum supportive measures at the discretion of the investigator
5. Grade 4 bronchospasm
6. Grade 3 bronchospasm not responding to medical intervention at the discretion of the investigator
7. Posterior reversible encephalopathy syndrome (PRES)
8. The investigator judges it necessary for medical reasons/non-compliance
9. The patient receives prohibited therapy and/or procedures during the trial, see Section [8.4.8](#)
10. Pregnancy
11. Patient/legal guardian withdraw consent to treatment
12. PD

Discontinuation criteria for IT

A patient should be discontinued from IT treatment if any of the following situations occur:

1. If the patient experiences neutropenia that causes a delay \geq 14 days after the first dose reduction by 20% of irinotecan and the second dose reduction by 20% of temozolomide
2. If the patient experiences thrombocytopenia that causes a delay \geq 14 days after the first dose reduction by 20% of irinotecan and the second dose reduction by 20% of temozolomide
3. If the patient does not meet the criteria to start the next cycle within 21 days after the planned subsequent cycle start date
4. Recurrence of \geq Grade 3 diarrhea despite maximal use of anti-diarrheals, prophylactic antibiotics, and a dose reductions of irinotecan of 20%
5. Recurrence of \geq Grade 3 regimen-related nausea and/or vomiting despite optimization of anti-emetic drugs and a dose reduction of IT by 20%
6. If \geq Grade 3 regimen-related dehydration recurs and persists for >3 days despite a dose reduction of IT by 20%

Discontinuation criteria for GM-CSF

A patient should be discontinued from GM-CSF treatment if any of the following situations occur:

1. Injection site reactions \geq CTCAE Grade 3
2. Allergic reactions (including anaphylactic reactions) \geq CTCAE Grade 3

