8.1.2 Treatment schedule

Please refer to [Appendix 2](#) if the patient has discontinued IT treatment due to toxicity.

Table 4 Treatment schedule

Treatment days in cycles of 21 days	-3 to 0	1	2	3	4	5	6	7	8	9	10	11-12	13-21
Premedication (8.4.1, 8.4.3)	X	X	X	X	X	X	X	X	X	X	X	X	
Irinotecan 50 mg /m ² /day (IV) + temozolamide 100 mg/m ² /day (orally) (8.1.2.1, 8.1.2.2)		X	X	X	X	X							
Naxitamab 2.25 mg/kg/day IV (9mg/kg/cycle) ¹ (8.1.2.3) ¹			X		X				X		X		
GM-CSF 250 ug/m ² /day s.c (8.1.2.4) ¹							X	X	X	X	X		

1) Patients achieving a CR or PR should receive 8 naxitamab cycles or 5 additional naxitamab cycles following the OR, whichever provides the longest treatment with naxitamab. Patients who have achieved a MR or SD at completion of the 8 cycles may receive naxitamab + GM-CSF consolidation treatment for 5 cycles administered at every 6 weeks

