11.2 Immunogenicity

Samples for assessment of anti-drug antibodies (ADA) should be sent to a special laboratory for analysis. Please refer to the laboratory manual for more information.

Table 10 ADA samples

ADA assessment: Prior to dosing in each cycle EOT	
• Anti-naxitamab antibodies*
---	--

*Analyses will be performed in batches. Therefore, results will not be available during the trial

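### The ORR-by-ADA subgroup table is classified partly by ADA samples taken after the four-cycle endpoint is fixed, in numbers that depend on outcome; the expected bias is probably upward for ADA-positive patients but of undetermined size.

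*Combined protocol and SAP*

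**What the plan says.** - **Endpoint.** Section 6.1 defines ORR as central CR or PR "at or before completion of four cycles". Section 9.1.2 places the C4 assessment before Day 1 of cycle 5.
- **Subgroup.** Section 12.11 lists twelve subgroup factors for the primary endpoint. One is "ADA status (negative at all times / positive at any time", with no time limit.
- **Sampling.** Table 10 in Section 11.2 takes ADA samples "Prior to dosing in each cycle" and at EOT. Samples are analysed in batches: "Therefore, results will not be available during the trial".
- **Progression.** Section 7.12 says "A patient should be discontinued from treatment with all IMPs if any of the following situations occur", and PD is on that list. Section 7.8 adds that "the patient should be called for EOT visit as soon as possible and before initiation of new anti-NB treatment".
- **Responders.** Under Section 7.2.1, CR/PR patients "should receive 8 naxitamab cycles or 5 additional naxitamab cycles following the objective response", whichever is longer.
- **MR/SD.** The Table 4 footnote in Section 8.1.2 says "Patients who have achieved a MR or SD at completion of the 8 cycles may receive naxitamab + GM-CSF consolidation treatment for 5 cycles". For ORR these patients are non-responders.
- **Deferred detail.** Section 12.13 leaves further detail to a separate SAP, whose text is not in the document supplied.

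**The concern.** There are two faults. First, a patient who first tests positive at cycle 7 is counted as ADA-positive in a table of responses that were settled at C4. Second, the number of chances to test positive depends on how the patient fared. Patients with early PD are non-responders, or nearly all so, and have the fewest samples. They therefore collect in the ADA-negative row even if ADA has no effect on response. This is a form of immortal-time bias.

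What is at stake is the reading of one table. Section 4.2 presents lower immunogenicity as a potential advantage of a humanized antibody. Section 4.3.2 says Trial 201 gave very limited information on efficacy in ADA-positive patients. Readers will look to this table on that question, and an upward bias could mask a real loss of response with ADA.

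**Working it through.** The plan gives no figure for this subgroup, so there is none to reproduce. The check is a model in which ADA has no effect on response.

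**Samples per patient.** A patient who starts n cycles has n post-baseline samples: pre-C2 to pre-Cn, plus EOT.
- PD after C2 or C4: 2 or 4 samples.
- Response at C2: max(8, 2+5) = 8. Response at C4: max(8, 4+5) = 9.
- MR/SD: 8, or 8+5 = 13 with full consolidation.

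**Inputs from the documents.**
- ADA incidence of 8.3% and 23.1% (Section 4.3.2).
- Mix A: 22 OR, 22 SD and 9 other of 53, from the dinutuximab plus IT follow-up study (Section 4.3.4).
- Mix B: 17 OR, 10 SD and 9 other of 36, from the naxitamab plus IT compassionate-use series (Section 4.3.4).

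**Assumptions.** Each post-baseline sample has the same chance h of first positivity. Responders are half at 8 and half at 9 samples; the other patients are half at 2 and half at 4. No patient is positive at baseline.

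**Formulas.** P(ever positive) = 1 − (1 − h)^k for k samples, with h solved to match the overall incidence. ORR by ADA status then follows from Bayes' rule.

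**Worked case: mix A, 8.3%, all SD stopping at C8.** h = 0.0117. P(positive) is 0.0955 for responders, 0.0902 for SD and 0.0348 for others.
- Overall: (22×0.0955 + 22×0.0902 + 9×0.0348)/53 = 4.398/53 = 0.083.
- ORR if positive: 22×0.0955/4.398 = 47.8%.
- ORR if negative: 22×0.9045/48.602 = 40.9%.
- Gap: +6.8 points before rounding.

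**Gap in points, ADA-positive minus ADA-negative, at 8.3% / 23.1% incidence.**

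| Share of SD reaching 13 cycles | Mix A | Mix B |
|---|---|---|
| None | +6.8 / +7.7 | +10.9 / +12.3 |
| Half | +0.8 / +1.5 | +5.6 / +7.0 |
| All | −4.1 / −3.9 | +1.2 / +2.2 |

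In mix A the sign changes when 57% to 63% of SD patients reach 13 cycles. In mix B it does not change with responders at 8 or 9 samples; with all responders at 8 and all SD at 13 it is −0.4 / +0.6. If half of responders also continue to 13, the gap with all SD at 13 is +1.2 / +1.7 (A) and +6.6 / +7.9 (B).

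**Plausible share reaching cycle 13.** C13 starts at about week 8×3 + 4×6 = 48, so one-year PFS is a rough guide. Spreading it pro rata over OR and SD patients is an assumption. The 37% in Section 4.3.4 gives 0.37×53/44 = 45% (A) and 0.37×36/27 = 49% (B), with gaps of +1.4 / +2.1 and +5.7 / +7.1. The 21% in Section 4.1 gives 25% and 28%, with gaps of +3.6 / +4.4 and +7.8 / +9.3. The upper confidence limit of 62.9% in Section 4.3.4 gives 76% and 84%, with gaps of −1.8 / −1.4 and +2.5 / +3.7.

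**Timing of conversion.** If h halves at each sample, the gap is +1.1 to +2.1 in both mixes. The share of ever-positive patients who first convert after the fourth post-baseline sample is 42% to 58% under constant h and 4% to 5% under halving.

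**Noise.** SE = √[p(1−p)(1/n₊ + 1/n₋)] with p = 0.415. With 52 patients, 4.3 positives give 24.8 points and 12.0 give 16.2. With 41 evaluable patients (Section 12.2), 3.4 and 9.5 positives give about 28 and 18. By the normal approximation Φ(gap/SE) at 52 patients, the ADA-positive row shows the higher ORR with probability 52% to 55% for a gap of 1 to 2 points, and 69% to 77% for 12 points.

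**Alternative rules.**
- First two post-baseline samples: gap 0.0 in every scenario, with 1.0 to 3.8 positives of 52 (constant h) or 3.4 to 9.8 (halving).
- First four post-baseline samples: gap +1.9 to +3.5 (constant) or +0.7 to +1.3 (halving).

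**The case against.** A reader might infer that the table is likely to show a falsely higher ORR in ADA-positive patients. The documents do not support that. They give no timing of naxitamab ADA, and early conversion leaves only 1 to 2 points. Against the standard error, the observed direction is often little better than a coin toss.

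Nor is the split simply responder against non-responder. Treating every non-responder as stopping at C2 or C4 would give +26 to +29 points, but MR/SD patients are planned for at least as many cycles as most responders. The contrast that matters is early PD against the rest.

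Further objections stand in part:
- Section 9.1.1 has local assessment decide whether treatment continues, with central review done retrospectively. Sampling therefore follows local response while the table reports central ORR. Discordance would be expected to weaken the bias, and the model ignores it.
- Exclusion criterion 6 bars prior anti-GD2 therapy only if PD occurred on it, so baseline ADA positivity is plausible. It would dilute the gap.
- The compassionate-use series had a median of 5 cycles, fewer than the model assumes. Putting 35% to 50% of OR and SD patients at 5 cycles in mix B, with the remaining SD at 8, still gives about +9 to +11, but the point values are not anchored.
- Section 12.7 plans a time-to-first-positive figure and ADA listings, and Section 12.4.1 plans response listings, so late conversions could be traced. The separate SAP may also set a cut-off.

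None of this removes the structural fault. The stated rule lets post-endpoint samples set the rows, and a SAP that only elaborates Section 12.11 would keep it.

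**Conclusion.** The point holds as a minor one. The any-time rule uses samples taken after the endpoint is fixed, and their number depends on outcome. With no true ADA effect, the expected bias is probably upward for ADA-positive patients: about +1 to +12 points in the illustrative cases, and near zero or negative if conversion is late and most SD patients complete consolidation. The size rests on assumed conversion timing, treatment lengths and borrowed response mixes; the documents do not fix it.

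The bias is small against an SE of 16 to 25 points (18 to 28 at 41 patients), and local-central discordance and baseline positivity would weaken it further. It affects one descriptive subgroup factor. The primary test, sample size and power do not use ADA status.

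**What to change.** For the ORR-by-ADA table only:
- **Main table.** Classify ADA from a common early window: baseline, pre-C2, and pre-C3 or the EOT sample that replaces it, in patients who reach the first response assessment. List patients without the full window separately, and state the timing of any EOT sample used.
- **Sensitivity table.** Use samples up to the C4 assessment, so that no post-endpoint sample sets a row. State whether the pre-C5 sample counts; the four-sample figures above include it.
- **Any-time status.** Keep it for the ADA incidence endpoint. Label any ORR table that uses it as descriptive and subject to this bias, to be read with the Section 12.7 figure.

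**Cost.** SAP wording only. The samples are already planned, and because ADA results are not available during the trial, the rule can be set before they are seen.

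**Downsides.** The early window has few ADA-positive patients (about 1 to 4 of 52 under constant conversion) and classes C3–C4 conversions as negative, although these could affect a C4 response. The C4 cut leaves about 2 to 3.5 points under constant conversion. In mix A with half of SD at 13 cycles it leaves about 2, against about 1 under the any-time rule, where opposite biases happen to offset. That is why the early window should be the main table.
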